### **2.9.2 Secondary efficacy analysis**

There are no secondary efficacy endpoints in this study.

### **2.9.3 Safety analysis**

#### Treatment Exposure

Frequencies of exposure to the study medication will be calculated based on the number of drops the subject has received over the course of the study. Frequencies of exposure will be categorized as the following: 1 drop and 2 drops. Frequencies of exposure will be summarized by treatment for the safety population defined in [Section 3.1](#), as well as for each gender group.

Compliance rates will be calculated by dividing the number of drops received by the number of drops that should have been given during the application of dose. Compliance rates will be summarized.

#### Early Termination

Subject disposition will be summarized by treatment and will be listed for those subjects who are terminated early. This listing will include demographic variables, treatment assigned, number of drops received, termination time, and the primary reason for early termination.

#### Adverse Events

Adverse events will be coded for preferred terminologies using Medical Dictionary for Regulatory Activities (MedDRA). AEs will be grouped into pre-treatment AEs, treatment-emergent AEs, and post-treatment AEs and will be reported separately, based upon the start date and time of the events compared to the start date and time of the treatment.

Adverse events will be defined as pre-treatment AEs if they occur prior to the treatment start date and time; as treatment-emergent AEs if they occur on or after the treatment start date and time and before the next day; and as post-treatment AEs if they occur after the treatment date.

Frequency of treatment-emergent AEs will be calculated for each body system, by preferred terminology, by treatment group, for number of subjects and percentage reporting the event.

The severity of the adverse events and the relationship to the investigational product will be summarized for each body system and preferred terminology by treatment group. Withdrawals due to adverse events will be summarized for each body system and preferred terminology by treatment group and will be listed with demographic variables for individual subjects.

Serious adverse events (SAE) (including deaths) will be listed for individual events.

Narratives will be provided for all deaths, non-fatal serious adverse events, and subjects withdrawn due to adverse events.

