### 1.2 *Potential Risks and benefits to human subjects*

Minimal risks are expected with AG-920. Based upon clinical trials conducted to date, expected risks for subjects may include temporary, mild conjunctival/ocular hyperemia, eye pain, instillation site reaction (stinging/burning), and conjunctival hemorrhage upon instillation of the investigational medicinal product (IMP). For any additional information on AG-920 use, please refer to the [Investigator's Brochure](#).

Minimal risks are expected with the comparator, Proparacaine HCl ophthalmic solution. Occasional temporary stinging, burning and conjunctival redness may occur with the use of Proparacaine. A rare, severe, immediate-type, apparently hyperallergic corneal reaction (characterized by acute, intense and diffuse epithelial keratitis, a gray, ground glass appearance, sloughing of large areas of necrotic epithelium, corneal filaments and, sometimes, iritis with descemetitis) has been reported. Allergic contact dermatitis from Proparacaine with drying and fissuring of the fingertips has also been reported. For any additional information on Proparacaine use, please refer to the [Package Insert](#).

As this study is to be conducted in healthy pediatric subjects, there is no anticipated benefit other than the possibility that a subject's participation in the present study may help others in the future to have more options for local anesthesia before ophthalmic procedures.

Any new, unexpected adverse events (AEs) present among subjects in this clinical trial will be communicated to Investigators and to ethics committees or Institutional Review Board (IRBs) in accordance with local regulations.

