**Secondary Endpoints**

Incidence of AEs, TEAEs, SAEs, withdrawals due to TEAEs

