**Table 1: Schedule of Visits and Procedures**

	Visit 1	Visit 2			Follow-Up
	Screening	Screening & Baseline			Phone call
	Day -2 - 0/1 Pre-dose	Day 1			Day 2-5
Procedures		Dose		2 -4 min post last drop	15-60 min post eye exam
		0 sec	30 sec		
Written Assent/Informed Consent	X				
Inclusion/Exclusion Criteria 	X	X 			
Demographics, Systemic and Ocular Medical History	X				
Concomitant Medication Query	X	-----X-----			X
Visual Acuity 	X 				X 
External Eye Exam	X				X
Biomicroscopy 					X 
Randomization		X 			
IMP Administration 		X	X 		
Eye Exam Procedure				X	
Adverse Event Assessment		-----X-----			X

IMP = investigational medicinal product

 Screening may occur on the same day as Visit 2 or up to 3 days previously. If on separate days, inclusion/exclusion criteria should be re-evaluated prior to dosing subject to ensure subject still qualifies.

 If Visit 1 and 2 are not performed on the same day, these assessments must be performed prior to dosing at 0 seconds.

 Age appropriate optotype (if capable) with clinically appropriate test (either Teller acuity charts, Allen pictures, HOTV letters, or Snellen acuity, per standard of care), or reaction to light (if not).

 Biomicroscopy only performed if necessary for a suspected AE

 One dose is 2 drops. First drop administered at 0 seconds and the second drop administered at 30 seconds (2 drops 30 seconds apart).

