### 8.3 Adverse events

All AEs occurring after the first dose of IMP and throughout the remainder of the study period (Follow-up Phone Call) will be considered TEAEs and must be documented on the relevant Electronic Data Capture (EDC) pages and in the source documents. Whenever possible, the diagnosis, if available, and not the symptoms should be reported as the AE. AEs and Serious Adverse Events (SAEs) will be coded according to the Medical Dictionary for Regulatory Activities (MedDRA).

Documentation of adverse events/adverse reactions includes start date and stop date, severity, action(s) taken, seriousness and outcome.

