### 9.4.8 Adverse Events

Verbatim descriptions of AEs will be mapped to MedDRA thesaurus terms and presented in a data listing. Treatment emergent AEs, those that occur after the first dose of study medication, will be summarized by treatment group using frequency counts and percentages for each System Organ Class (SOC) and Preferred Term (PT) within each SOC. Summaries will be presented separately for ocular and non-ocular AEs. These summaries will also be presented by the relationship to the

Investigational Medicinal Product (related, unrelated) and by severity of the AE (mild, moderate, severe). Fisher's exact test will be used to test the difference in proportions of subjects with each AE between treatment groups (SOC and PT).

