##### Safety Population

The safety population is defined as all subjects who are randomized and who have received at least one drop of the dose (2 drops) of study medication. The safety population will be utilized for comparative safety analyses among treatment groups.

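### The SAP closes the treatment-emergent AE class at the end of the dosing day, contradicting both the protocol, which runs it to the Day 2-5 call, and the SAP's own onset-time tables

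*SAP*

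**What the plan says.** **Protocol.** Section 8.3 states: "All AEs occurring after the first dose of IMP and throughout the remainder of the study period (Follow-up Phone Call) will be considered TEAEs". Section 6.4.4 places that call on Days 2-5, 24 to 96 hours after dosing. Section 9.4.8 repeats the class with no closing point: "Treatment emergent AEs, those that occur after the first dose of study medication, will be summarized by treatment group". It then asks for those summaries by relationship and severity ("related, unrelated) and by severity of the AE (mild, moderate, severe"). The secondary endpoint in Section 2 is "Incidence of AEs, TEAEs, SAEs, withdrawals due to TEAEs".

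**SAP 2.9.3, Adverse Events.** Three separately reported classes are set up by onset: pre-treatment, treatment-emergent and post-treatment. The middle one is defined "as treatment-emergent AEs if they occur on or after the treatment start date and time and before the next day". Anything starting after the treatment date goes to the third class.

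**SAP 5.3 and SAP 7.** Section 5.3 tabulates TEAEs by onset on the dosing day against onset after it (Tables 4.3.1-4.3.3). It limits the severity and relationship table (4.4.1) and the early-termination and SAE tables (4.4.2-4.4.7) to TEAEs. The table list in Section 7 holds a post-treatment AE table, 4.2.4, which the text of 5.3 does not describe.

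**The concern.** An AE that begins on Day 2 is a TEAE under Protocol 8.3 and is not one under SAP 2.9.3. The SAP gives no reason for narrowing a class that the protocol had already defined. Nor can a programmer satisfy the whole SAP: Tables 4.3.1-4.3.3 presuppose the protocol's window, while 2.9.3 and Table 4.2.4 presuppose a window that ends at midnight.

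TEAE incidence and withdrawals due to TEAEs are named components of the secondary endpoint, so class membership is part of the endpoint's definition. The follow-up call exists to ask about AEs and medication changes. Under 2.9.3, no event it uncovers with onset after Day 1 could enter a TEAE table. The TEAE count would then be lower than the protocol's definition gives, and those events would lack the severity and relationship summary that Protocol 9.4.8 requires.

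**Working it through.** The plan states no figure to reproduce. The check is a comparison of definitions, followed by a count of tables and the weight of one subject.

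**1. Classification by onset**

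| AE onset | Protocol 8.3 | SAP 2.9.3 | SAP Tables 4.3.1-4.3.3 |
|---|---|---|---|
| Day 1, after dosing | TEAE | TEAE | TEAE, dosing day |
| Day 2 up to the call | TEAE | Post-treatment AE | TEAE, after dosing day |
| After the call | Outside the stated window | Post-treatment AE | TEAE, after dosing day, if taken literally |

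The second row is the conflict. SAP 2.9.3 disagrees there with the protocol and with SAP 5.3.

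**2. Tables affected if the 2.9.3 class is applied**

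- TEAE incidence tables that lose later onsets through the 2.9.3 definition alone: 4.2.2, 4.2.3 (terms above 5%), 4.2.5 and 4.2.6 (by eye) = 4.
- Tables that lose them because 5.3 restricts them to TEAEs: 4.4.1 to 4.4.7 = 7.
- Total: 4 + 7 = 11.
- Tables with a category that can never be filled: 4.3.1, 4.3.2 and 4.3.3 = 3.

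The second line needs both sections. The severity, relationship and withdrawal sentences in 2.9.3 speak of adverse events without the treatment-emergent qualifier; the restriction comes from 5.3.

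**3. Weight of one subject**

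Inputs, from the Protocol Summary and Section 9.2: about 30 evaluable subjects per group, and up to 70 randomized 1:1, that is 70/2 = 35 per group. Each subject whose only AE begins between Day 2 and the call changes the arm's TEAE incidence by

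- 1/35 = 2.86 percentage points, or
- 1/30 = 3.33 percentage points.

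How many such subjects there will be cannot be computed: the documents give no AE rates or onset times.

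**4. What remains for later-onset AEs**

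Table 4.2.4 gives incidence by preferred term. Tables 4.1.1 and 4.1.2 are titled as overall summaries of adverse events, not of TEAEs. The AE listings remain, and deaths, other SAEs and AE withdrawals receive narratives. Among the titled tables, none gives severity or relationship for the post-treatment class.

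**The case against.** The strongest reply is that nothing is lost. Later AEs stay in Tables 4.2.4, 4.1.1 and 4.1.2, in the listings and in the narratives, and the AE and SAE components of the secondary endpoint do not depend on the TEAE window. The protocol describes the expected reactions as occurring on instillation (for example "instillation site reaction (stinging/burning), and conjunctival hemorrhage upon instillation"), so most should fall on Day 1 under either rule. The three discontinuation tables have little to lose, because only the phone call remains after Day 1. All of this stands and limits the reach. It does not remove the conflict over which events count as TEAEs.

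Four stronger readings are tempting, and the documents do not support them.

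- *The start boundaries also conflict.* Table 1 of the protocol says "One dose is 2 drops. First drop administered at 0 seconds and the second drop administered at 30 seconds", so a reader might infer that the protocol's phrase about the first dose excludes an AE between the drops, or any AE in a one-drop subject. In a single-dose trial that phrase ordinarily means once dosing has begun. Both documents place one-drop subjects in the Safety Population (in the SAP, "all subjects who are randomized and who have received at least one drop of the dose (2 drops) of study medication"), which the protocol uses to summarize safety. Denying those subjects any TEAE would defeat that purpose.
- *Most of the follow-up window is cut off.* The share of hours excluded depends on the clock time of dosing, which the documents do not give. It would measure time, not events.
- *Section 2.9.3 by itself removes later AEs from the severity and withdrawal summaries.* It does not; that loss arises only in combination with 5.3.
- *The absence of table shells shows that the plan leaves the point open.* SAP 7 says shells follow the text, and SAP 10 says they are available on request. Their absence from the copy reviewed proves nothing.

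**Conclusion.** The conflict is real and rests on the text alone. SAP 2.9.3 contradicts Protocol 8.3 on when the TEAE class ends, is narrower than Protocol 9.4.8, and makes one category of SAP Tables 4.3.1-4.3.3 empty by definition. Followed as written, 2.9.3 can only lower the TEAE count relative to Protocol 8.3, by about 2.9 to 3.3 points of an arm's incidence per affected subject, assuming 30 to 35 subjects per arm. The number of affected subjects is unknown and may be small.

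This should be fixed, but its consequences are limited: no data are lost and the primary endpoint is unaffected. A reader might infer that later AEs go unreported; the documents do not support that. They are reported under another class, with less detail.

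**What to change.** - In SAP 2.9.3, define TEAEs as AEs with onset from the treatment start date and time through the Follow-up Phone Call, matching Protocol 8.3.
- Keep Tables 4.3.1-4.3.3. Their split of dosing-day against later onset then becomes informative.
- Redefine the post-treatment class and Table 4.2.4 as onset after the call, and do not drop them. Protocol 8.3.3 requires SAE reporting up to four weeks after the last administration, well past the Day 2-5 call. Without this class, an SAE starting in that interval would have no class and no table.
- Align the severity, relationship and withdrawal wording in 2.9.3 with the TEAE wording in 5.3.

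The cost is one SAP definition, one redefined table and some wording. No new data, change in sample size or clinical change is involved. The reported TEAE rate may be slightly higher. The change should be made before AE data are tabulated, since treatment is masked only to subjects and their parents or guardians.

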#### Visual Acuity and External Eye Exam

Age-appropriate visual acuity tests and external eye exam will be summarized for abnormality by treatment for the screening (pre-dose) and Day 1 (post-dose), using frequency and percent. The analysis will be based on the safety population defined in [Section 3.1](#).

Where applicable, for both study eye and fellow eye, abnormal findings of visual acuity and external eye exam at screening and post-dose will be analyzed, respectively, for differences between AG-920 and active-control groups, using a Chi-square test.

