## Summary

Study Number	AG-920-CS304	
Clinical Phase:	Phase 3	
Type of study	Efficacy and Safety	
Name of Investigational product:	Articaine Sterile Topical Ophthalmic Solution (AG-920)	
Name of Comparator product	0.5% Proparacaine Hydrochloride	
Duration of treatment per subject	1 day	
Objectives and Endpoints:	Primary Objective	Primary Endpoints
	To evaluate anesthetic efficacy of AG-920	The proportion of subjects in which an eye exam was able to be performed
	Secondary Objective	Secondary Endpoints
	To evaluate the safety and tolerability of AG-920	Incidence of AEs, TEAEs, SAEs, withdrawals due to TEAEs
Subject Population:	Healthy pediatric volunteers Exclusion criteria may be found in Section 4.2.	
Design:	Randomized, active-controlled, single-masked, parallel-group.	
Visit Schedule:	Study visits will consist of a Screening Visit, a dosing and eye exam visit, and a follow-up phone call	
Number of Investigational Sites:	1-3 US sites	
Estimated Total Sample Size:	Enroll up to 70 subjects to result in 60 evaluable subjects; ~30 per treatment group	
Plan for Data Analysis:	The sample size is as directed by the U.S. FDA for a Pediatric Study Plan.	
Investigational/Comparator Product(s), Dose and Mode of Administration	Subjects will receive a single dose (two drops) of IMP in one (study) eye. The IMP will be randomized as either AG-920 or Proparacaine HCl Ophthalmic Solution. The study eye will be randomized as either right eye (OD) or left eye (OS). The single dose will be administered by the clinic staff.	

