### 1.3 *Design justification*

#### **Route of administration, dosage, dosage regimen, and treatment period(s)**

The dose selected for this study is based on clinical experience with this molecule by another route (dental) or from outside the United States, and preclinical safety studies. The positive-control design is as discussed with the U.S. FDA for ethically and scientifically appropriate investigation in the pediatric population. For more details, please refer to the [Investigator's Brochure](#).

The selected dose of the investigational medicinal product AG-920 is 8% Articaine Sterile Topical Ophthalmic Solution which contains 80 mg/mL of Articaine Hydrochloride (HCl).

The intended route of administration for AG-920 (testing treatment) and Proparacaine HCl Ophthalmic Solution (active-control or reference treatment) is topical ocular in this study. Each dose of AG-920 or Proparacaine HCl will consist of two drops 30 seconds apart in the study eye.

This study consists of a single treatment and subjects will be randomized 1:1 to AG-920 or Proparacaine HCl Ophthalmic Solution.

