### 9.2 Sample Size Considerations

The sample size of approximately 70 subjects to be randomized in a 1:1 allocation ratio for AG-920 and reference groups is as directed by the U.S. FDA for a Pediatric Study Plan, rather than being estimated based on a pre-defined non-inferiority margin commonly used for the trial design of therapeutical equivalence. The Sponsor plans to enroll up to 70 subjects in order to obtain at least 60 evaluable subjects.

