## 5.4 Visual Acuity and External Eye Exam

Frequency and percent of visual acuity abnormality will be presented by treatment for the pre-dose (screening) and post-dose assessments in [Table 5.1.1](#) for the study eye.

Frequency and percent of visual acuity abnormality will be presented by treatment for the pre-dose (screening) and post-dose assessments in [Table 5.1.2](#) for the fellow eye.

Frequency and percent of eye exam abnormality will be presented by treatment for each category of iris, pupil, and lens at the pre-dose (screening) and post-dose assessments in [Table 5.2.1](#) for the study eye.

Frequency and percent of eye exam abnormality will be presented by treatment for each category of iris, pupil, and lens at the pre-dose (screening) and post-dose assessments in [Table 5.2.1](#) for the fellow eye.

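### Visual acuity and external eye exam abnormalities are compared separately at screening and post-dose without linking the two within a child, so pre-existing findings can blur new ones, mainly for acuity

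*SAP*

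**What the plan says.** Under Visual Acuity and External Eye Exam, SAP 2.9.3 states that these measures "will be summarized for abnormality by treatment for the screening (pre-dose) and Day 1 (post-dose), using frequency and percent". A second paragraph adds the testing: "abnormal findings of visual acuity and external eye exam at screening and post-dose will be analyzed, respectively". Each eye of the child is covered, treated or not. The arms are to be compared by one stated method, namely "for differences between AG-920 and active-control groups, using a Chi-square test". These are two separate between-arm comparisons, one before treatment and one after it.

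SAP 5.4 follows the same layout: "Frequency and percent of visual acuity abnormality will be presented by treatment for the pre-dose (screening) and post-dose assessments". It treats the external exam alike, by iris, pupil and lens. The titles of Tables 5.1.1 to 5.2.2 announce summaries of abnormalities only. No visible section plans a screening-by-post-dose cross-tabulation, a newly abnormal category, or adjustment for the screening result.

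Protocol 9.4.7 plans only summaries of these measures. For adverse events, protocol 9.4.8 says: "Fisher's exact test will be used to test the difference in proportions of subjects with each AE between treatment groups".

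**The concern.** The safety question is whether the drops changed the eye. Both assessments are made before and after dosing in both eyes (protocol Table 1 and section 6.1; SAP 2.6.3), so each child's own starting point is known. The planned post-dose test does not use it.

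The screening test does not make up for this. It compares randomized arms before any drug is given, so a difference there is due to chance and says nothing about safety. Showing the two sets of percentages side by side gives only the margins: new abnormalities in some children can be offset by resolved ones in others.

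At stake is the ability of two named safety measures (protocol 8.1, SAP 2.6) to show a change caused by the drug. No efficacy claim or decision rule depends on them.

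**Working it through.** **Inputs from the documents.** Arm size is about 30 (protocol Summary: "Enroll up to 70 subjects to result in 60 evaluable subjects; ~30 per treatment group"), or 35 if all 70 are randomized 1:1. The level is two-sided 0.05 (protocol 9.4.1). Acuity is an exclusion only if corrected vision is worse than 20/200, or there is no reaction to light in children who cannot read optotypes (protocol 4.2).

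**Assumptions.** The documents give no rate of abnormality before or after dosing, so pre-existing and new rates are assumed and varied. They also give no power figure for this analysis, so there is none to reproduce.

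**Step 1: fixed counts.** Let b children per arm be abnormal at screening and stay so, and let 6 become abnormal on AG-920 and 0 on proparacaine. With n = 30:
- The planned test compares (b + 6)/30 with b/30 by uncorrected Pearson chi-square.
- The new-abnormality test compares 6/(30 − b) with 0/(30 − b). Its two-sided Fisher P is 2 × C(m,6)/C(2m,6), where m = 30 − b.

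| b per arm | Planned comparison | Chi-square P | New abnormalities | Fisher P |
|---|---|---|---|---|
| 0 | 6/30 vs 0/30 | 0.010 | 6/30 vs 0/30 | 0.024 |
| 1 | 7/30 vs 1/30 | 0.023 | 6/29 vs 0/29 | 0.023 |
| 2 | 8/30 vs 2/30 | 0.038 | 6/28 vs 0/28 | 0.023 |
| 3 | 9/30 vs 3/30 | 0.053 | 6/27 vs 0/27 | 0.023 |
| 6 | 12/30 vs 6/30 | 0.091 | 6/24 vs 0/24 | 0.022 |

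The crude difference is 6/30 = 20 points in every row. The P value rises only because the pre-existing cases add variance. The planned test first exceeds 0.05 at b = 3, which is 3/30 = 10% pre-existing. At 35 per arm, b = 6 gives 0.101 (planned) and 0.024 (Fisher).

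**Step 2: power.** Let a fraction b be abnormal at screening, and let new-abnormality rates among the rest be 20% and 2%. The crude difference is (1 − b) × (0.20 − 0.02). At b = 0.2 this is 0.8 × 18 = 14.4 points. Power at 30 per arm (planned test by exact enumeration, new-abnormality tests by 20,000 simulations):

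| Pre-existing | Crude difference | Planned chi-square | New abnormalities, chi-square | New abnormalities, Fisher |
|---|---|---|---|---|
| 0% | 18.0 points | 69% | 69% | 41% |
| 10% | 16.2 points | 35% | 62% | 44% |
| 20% | 14.4 points | 23% | 55% | 40% |
| 30% | 12.6 points | 17% | 47% | 34% |
| 50% | 9.0 points | 11% | 29% | 17% |

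The two chi-square columns isolate the effect of using the screening result: nothing at 0%, and 55% against 23% at 20%. With no pre-existing findings, changing to Fisher lowers power from 69% to 41%.

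**Step 3: choice of test.** By exact enumeration, the chi-square type I error peaks at 5.5% (30 per arm) or 5.7% (35 per arm). At a 1% event rate and 30 per arm it is 0.03%. Single sparse tables can differ: 4/30 vs 0/30 gives 0.038 by chi-square and 0.112 by Fisher.

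**The case against.** **New changes are captured elsewhere.** Protocol 8.3.1 counts as adverse events both conditions newly detected after dosing and worsening of existing ones. Adverse events are assessed alongside the post-dose acuity and external exam (protocol 6.4.3.2), and the SAP tabulates them separately for study and fellow eye. The secondary endpoint is adverse event incidence, and acuity and eye exam data are listed by child. A reader might infer that the plan would hide ocular harm altogether; the documents do not support that. What stands against the objection is that an adverse event record depends on the investigator reporting it, and listings leave the matching to the reader. Neither fully replaces an analysis of change in measures named as safety parameters.

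**Pre-existing abnormality may be rare.** These are healthy children with a normal cornea, and nystagmus and current inflammation are excluded. This largely stands for the external exam, where frequent findings in iris, pupil or lens are not obviously expected. It is weaker for acuity: the children already have a planned ophthalmic examination, and the acuity limit is wide.

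**Sparse tables.** A reader might also infer that chi-square P values on rare findings are unreliable and must be replaced. The check does not bear that out: the type I error is at most 5.5% to 5.7%, and in a safety screen Fisher's test makes a rare signal harder to see. The choice is largely preference. Sparseness and blurring also tend to affect different tables, since one needs few findings and the other needs many.

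**What cannot be seen.** The acuity procedure and much of the exam procedure are redacted, and table shells are available only on request, so how an abnormal result is defined cannot be checked. SAP 2.9.3 also limits testing to where it applies, which leaves some discretion.

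**Conclusion.** The point holds as a low-cost improvement to a secondary safety analysis. The planned comparisons ignore screening information already collected on the same eye, and the screening-visit test has no safety purpose. Under the assumed 6 versus 0 new abnormalities at 30 per arm, the planned P value moves from 0.010 to 0.091 as pre-existing cases go from 0 to 6 per arm, while the new-abnormality Fisher P stays at 0.022 to 0.024. The planned test loses significance only from about 10% pre-existing abnormality. Below that, little or nothing is lost.

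All abnormality rates here are assumptions. The case is strongest for acuity and weak for the external exam. It does not show that the chi-square test is invalid or that new ocular changes would go unrecorded.

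**What to change.** In SAP 2.9.3 and 5.4 and Tables 5.1.1 to 5.2.2:
- For each arm and eye, cross-tabulate screening by post-dose status (normal or abnormal).
- In place of the crude post-dose test, compare the proportion newly abnormal among children normal at screening, with a 95% CI for the difference.
- Drop the screening-visit test and keep its counts as description.
- If a P value is kept, an exact test would match protocol 9.4.8. This is optional.
- Add a worsened category only where the same acuity test is used at both times and worsening is defined in advance. Protocol Table 1 allows several acuity tests and light reaction, so a common definition cannot be assumed.

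The cost is SAP wording, table layout and slightly smaller denominators (24 instead of 30 per arm if 6 are abnormal at screening). No new data are needed.
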